5.2 Exclusion criteria

1. Histologically confirmed BE with high-grade dysplasia.
2. Histologically confirmed diagnosis of invasive carcinoma of the esophagus.
3. Histologically confirmed BE with low-grade dysplasia that has been diagnosed by at least two expert gastrointestinal pathologists.
4. Prior endoscopic therapy for Barrett's esophagus, including (but not limited to) mucosal resection, radiofrequency ablation, and photodynamic therapy.
5. A relevant history of esophageal or gastric surgery that, in the investigator's opinion, could compromise the objectives of the trial.
6. History of atrophic gastritis, pernicious anemia, or Zollinger-Ellison syndrome.
7. Participation in a trial of an IMP within the previous 28 days.

8. Prolonged QTc interval (>450 msec)
9. History of allergic reactions attributed to compounds of similar chemical composition to YF476.
10. History or baseline findings of:
 - diabetes mellitus requiring insulin therapy;
 - pancreatitis (baseline amylase and/or lipase $\geq 2.0 \times$ ULN);
 - hepatitis B or hepatitis C;
 - HIV, unless, at the discretion of the PI, with at least 120 days on stable ART with undetectable HIV viral load and CD4 >350 cells/mm³;
 - malabsorption syndrome or inability to swallow or retain oral medicine;
 - major surgery ≤ 28 days prior to enrollment;
 - ECOG performance status ≥ 2 ; or
 - cancer within 3 years except for basal carcinoma of the skin or cervical carcinoma in-situ.
 - Also, any clinically significant and uncontrolled major morbidity including but not limited to: serious cardiac disease (unstable angina, s/p myocardial infarction ≤ 1 month); respiratory disease (advanced COPD or pulmonary fibrosis); uncontrolled hypertension; active systemic infection; or psychiatric illness/social situations that would limit compliance with study requirements.
11. Certain medicines and herbal remedies (see Appendix B) taken during the 7 days before the start of study drug.
12. A history of cancer >3 years from the time of enrollment, and the patient is not up to date with surveillance for that cancer (based on national guidelines), or has evidence of cancer at the time of enrollment.

5.3 Inclusion of women and minorities

Men and women of all races and ethnic groups are eligible for this trial. However, the described epidemiology of Barrett's esophagus is such that the majority of study patients are likely to be white males.

5.4 Recruitment and retention plan

There will be 2 study sites: Columbia University Medical Center (CUMC), New York, US, and the National Institute for Health Research (NIHR) Clinical Investigation Ward (CIW), Cambridge University Hospitals, Cambridge, UK. Eligible patients will be recruited from the clinical practices of the study investigators ([name]). All of the study investigators see a large volume of patients referred for management and treatment of Barrett's esophagus. We aim for 20 patients to complete the trial. Recruitment progress will be assessed on an ongoing basis. Screening and enrollment logs will be regularly reviewed by the investigators. Patient withdrawals will be

carefully monitored. Methods for patient retention will be implemented, including the maintenance of regular contact with study patients. The study staff will meet regularly to review issues related to recruitment and retention, identify areas of improvement, and implement appropriate strategies to address any deficiencies. Additional recruitment methods such as advertising may be performed by each individual site with the approval of that site's Institutional Review Board or REC.

Withdrawals will be replaced at the discretion of the investigator.

6 Administration of study medication

Study medication will be dispensed on an outpatient basis, and self-administered by patients. Reported adverse events and potential risks are described in Section 4.3.

6.1 Dose regimen and dose groups

- Patients will take 25 mg YF476 (1 x 25 mg capsule) or matching placebo capsules, by mouth once daily.
- The treatment period for this trial will be 12 weeks.

6.2 YF476 administration

- Each study patient will self-administer the YF476 or placebo.
- The study medication will be dispensed into bottles: 46 capsules of 25 mg YF476 or placebo per bottle. 1 bottle will be dispensed to participants at the baseline visit (Visit 2) and at the Week 6 visit.
- Study medication should be taken once daily, in the morning, with breakfast. But, if a patient takes the study medication without food, or at a different time of the day, it will not be recorded as a protocol deviation. Missed doses will be recorded as protocol deviations.

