8.2 Baseline testing and pre-study evaluation

Visit 1: registration

Patients will attend the clinic and complete the informed consent form. The investigator will complete the following evaluation for each patient, and enter the data from this visit, and all subsequent visits, on the appropriate page of the CRF:

- review of most recent endoscopy (within 3 years) to confirm diagnosis of Barrett's esophagus with no dysplasia;
- review of medication history to determine that participants meet the inclusion criteria (daily PPI use for at least the most recent 12 months before study entry, and stable PPI dose for at least the most recent 3 months before study entry);
- medical history, physical examination, ECG and vital signs;
- blood and urine samples for laboratory safety tests; and
- urine pregnancy test (pre-menopausal women only).

Visit 2: baseline

Visit 2 may occur on the same day or up to 2 weeks after Visit 1. The patient will fast for 6 hours before the study visit. The investigator will complete the following evaluation for each patient, and enter the data from this visit, and all subsequent visits, on the appropriate page of the CRF. If Visits 1 and 2 are combined, only 1 blood sample (safety tests, fasting serum gastrin, plasma CgA and serum for storage) and 1 urine sample will be taken, and ECG, vital signs and pregnancy tests will be done only once.

- blood and urine samples for laboratory safety tests, urine pregnancy test (pre-menopausal women only), ECG and vital signs;
- blood samples for fasting serum gastrin, plasma CgA and serum for storage;
- endoscopy and biopsies; and
- randomization to 25 mg YF476 or placebo, and dispensing of study medication (a 42-day supply, plus overage: 1 bottle of 25 mg YF476 or placebo containing 46 capsules).

The investigator will then:

- give the patient a diary card;
- tell the patient to start taking their study medication the day after Visit 2;
- remind the patient to fast before the Week 6 visit (6 weeks after starting study medication); and
- remind the patient not to take their study medication at home on the day of the Week 6 visit, but instead to bring their container of study medication with them to the visit, and take their dose at the clinic, after the fasting blood tests.

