8.3 Evaluations during study treatment

Week 6 visit: after 6 weeks of study treatment

The investigator will:

- check that the patient has fasted;
- collect the diary card, and issue a new one;
- check the diary card for compliance with treatment, and for adverse events and concomitant medication;
- collect the study medication bottle and assess compliance;
- do an ECG and vital signs;
- take blood and urine for laboratory safety tests and urine pregnancy testing (pre-menopausal women only);
- take blood samples for fasting serum gastrin, plasma CgA, trough YF476 concentration and serum for storage;
- after taking the fasting blood samples, give the patient their dose of study medication, wait 1 h, then collect blood for assay of peak concentration of YF476;
- issue a new container of study medication, to be taken as before;
- remind the patient to fast before the next visit; and
- remind the patient not to take their study medication at home on the day of the Week 12 visit, but instead to bring their container of study medication with them to the visit, and take their dose at the clinic, after the fasting blood tests and endoscopy.

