8.6 Flexibility of study days

There will be a ± 4 day window for clinic visits.

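### The second 46-capsule bottle does not cover an early Week 6 visit followed by a late Week 12 visit, even when both are within the ±4 day window

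*Protocol*

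**What the plan says.** Dosing is one capsule a day (Protocol 6.1), and at Visit 2 the investigator is to "tell the patient to start taking their study medication the day after Visit 2" (8.2). Section 6.2 specifies "46 capsules of 25 mg YF476 or placebo per bottle" and adds that "1 bottle will be dispensed to participants at the baseline visit (Visit 2) and at the Week 6 visit". Section 8.2 explains the fill as "a 42-day supply, plus overage: 1 bottle of 25 mg YF476 or placebo containing 46 capsules".

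Section 1.6 times the Week 6 and Week 12 visits each from the start of study treatment. Section 8.6 then says "There will be a ± 4 day window for clinic visits", without saying what the window is measured from. SAP section 12.3 repeats the window.

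At Week 6 the patient takes that day's dose in clinic from the container brought along (8.2). The investigator is to "collect the study medication bottle and assess compliance" and to issue a new container (8.3). The schedule in 8.1 also shows collection at Week 6. Nothing returns leftover capsules to the patient; sections 7.5 and 7.8 send unused supplies back to the supplying pharmacy. At Week 12 the trough YF476, gastrin and CgA samples come first, then the endoscopy and biopsies, then the clinic dose, then the 1-hour peak sample (8.4).

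**The concern.** An overage of 4 capsules on a 42-day supply looks matched to a ±4 day window, and it is enough for one window. The second bottle, however, spans the time between two visits that can each move by 4 days. If Week 6 is early and Week 12 is late, that time grows by up to 8 days.

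Any shortfall comes at the end of the second bottle, at the Week 12 visit. That visit provides the primary Ki67 biopsy, the second trough and peak YF476 samples, and the Week 12 gastrin and CgA. A patient who attended every visit within window could be without a capsule for the clinic dose or, less often, off drug for some days before the biopsy. With 10 patients per arm planned and YF476 concentrations informative only on active treatment, one such patient would be noticeable in the PK summary.

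**Working it through.** **The plan's own figure.** 6 weeks × 7 days = 42; 42 + 4 = 46. The fill reproduces as a six-week supply plus one 4-day window.

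**Calendar.** Let Day 1 be the first dose, the day after Visit 2. Six weeks later is Day 43 and twelve weeks later is Day 85. Write d6 and d12 for the visit offsets, each a whole number from −4 to +4. Week 6 then falls on Day 43 + d6 (Days 39 to 47) and Week 12 on Day 85 + d12 (Days 81 to 89). There are 9 × 9 = 81 offset pairs.

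**First bottle.** It covers Days 1 to 46. Counting the Week 6 clinic dose, the need is 43 + d6, at most 47. On Day 47 the new bottle is issued at the same visit, so no day is missed.

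**Second bottle.** From the day after Week 6 up to and including the Week 12 clinic dose:

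need = (85 + d12) − (43 + d6) = 42 + k, where k = d12 − d6.

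The number of pairs giving a difference k is 9 − |k|. The shortfall is k − 4 capsules. The last of these is the clinic dose, taken after the biopsy, so the doses missed before the biopsy number k − 5.

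| k (days) | Offset pairs | Capsules needed | Short of 46 by | Doses missed before biopsy | Days from last dose to biopsy |
|---|---|---|---|---|---|
| 4 or less | 71 | 46 or fewer | 0 | 0 | 1 |
| 5 | 4 | 47 | 1 | 0 | 1 |
| 6 | 3 | 48 | 2 | 1 | 2 |
| 7 | 2 | 49 | 3 | 2 | 3 |
| 8 | 1 | 50 | 4 | 3 | 4 |

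- No capsule for the Week 12 clinic dose: 4 + 3 + 2 + 1 = 10 of 81 pairs (12%).
- At least one dose missed before the biopsy: 3 + 2 + 1 = 6 of 81 pairs (7%).

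**Worst case.** Week 6 on Day 39, Week 12 on Day 89. The second bottle starts on Day 40 and lasts 46 days, through Day 85. Days 86, 87 and 88 are missed, and there is no capsule for the clinic dose on Day 89.

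**One window at a time.** Week 6 on time and Week 12 four days late needs 46. Week 6 four days early and Week 12 on time also needs 46. Both are covered.

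**Total supply.** The second bottle lasts at least through Day 39 + 46 = Day 85, so at least 85 days of drug are supplied, against the 84 days of the 12-week period.

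**Sensitivity to the reading.**
- Nominal visit days of 42 and 84 give the same counts (10 and 6) and the same worst-case gap.
- If the Week 6 clinic dose came from the second bottle, the counts rise to 15 and 10, and the worst case is 4 missed doses with the last dose 5 days before the biopsy. Section 8.2 points to the first bottle instead.
- If patients kept their leftovers there would be no gap: 2 × 46 = 92 capsules against at most 89 doses.
- If the Week 12 window ran from the actual Week 6 visit, the interval would be at most 42 + 4 = 46 days and there would be no gap.

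**The case against.** The case for leaving this alone is reasonable. The overage handles a 4-day slip at either visit and fails only when the two slips oppose each other. A patient whose visits tend to run early or late together is less likely to be affected, and each dose skipped from the second bottle leaves a spare capsule. Section 8.6 does not state the anchor of the window, and a clinic that books Week 12 from the actual Week 6 date never meets the problem. The full 12-week course is supplied in every case. These points stand and they limit the size of the issue. They do not remove it, because section 1.6 times both visits from treatment start and nothing caps the interval between them.

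Some stronger readings are tempting, and the documents do not support them:

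- A reader might count the first bottle as short, since 43 + 4 = 47. The new bottle is issued on that day, so no dose is missed.
- A reader might take all 10 pairs as patients off drug at the biopsy. In 4 of them only the capsule due after the biopsy is missing, and the biopsy and trough sample are unaffected.
- A reader might take the 4-day figure as four doses missed before the biopsy. It is the time since the last dose, normally 1 day; three doses are missed, in one pair of 81.
- A reader might treat every uncovered day as a missed-dose deviation under section 6.2. Those days fall after the 84-day course, and the section does not say whether they count.
- A reader might argue from the 7 h half-life in section 3.2.2 that 96 h is about 14 half-lives (96/7 = 13.7). That half-life is for 100 mg in a single-dose study, and an ordinary 24 h trough is already about 3.4 (24/7). It bears on the trough sample. The documents give no time course for Ki67 after stopping drug, so it shows nothing about the primary endpoint.

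**Conclusion.** The point holds as a low-severity inconsistency: the stated fill does not cover the protocol's own windows when Week 6 is early and Week 12 is late. The second bottle can be up to 4 capsules short.

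The 12% and 7% are shares of possible offset pairs. They become probabilities only if offsets are uniform and independent and adherence is perfect, none of which the documents state. On those assumptions about 20 × 6/81 = 1.5 of 20 patients would miss a dose before the biopsy, or 10 × 6/81 = 0.7 on active drug. Visits kept closer to schedule would make it fewer.

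The conclusion also rests on both windows being measured from treatment start and on first-bottle leftovers not going back to the patient, which is the plain reading of sections 1.6, 8.1 and 8.3. The clearest consequence is for Week 12 PK: no peak sample after a dose, or a trough that is not a 24 h trough. The effect on the Ki67 comparison cannot be quantified from the documents and is probably small.

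**What to change.** Reconcile Protocol sections 1.6, 6.2, 8.2, 8.3 and 8.6 so that every permitted pair of Week 6 and Week 12 dates is supplied through the Week 12 clinic dose. Any one of three items could be brought into line: the bottle fill, the handling of leftover capsules at Week 6, or the anchor of the Week 12 window. Which of them changes is for the sponsor. If the window wording changes, SAP section 12.3 should follow it.

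The cost is a few capsules per patient or one clarifying sentence. Sample size and analysis are unaffected.

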The pharmacokinetic profile of YF476 varied among the 1996, 2001, 2005 and 2009 capsule formulations. The 2001 and 2005 formulations were crystalline, and the 1996 and 2009 formulations were spray-dried. The spray-dried formulations had the most favourable profile. In a single-dose study of 50–400 mg of the current (2009) formulation of YF476, absorption was rapid, T_{max} was 1.5–2 h, $T_{1/2}$ varied with dose, and C_{max} and AUC_{0-24} were not proportional to dose. $T_{1/2}$ after 100 mg YF476 was about 7 h. Food increased C_{max} and AUC_{0-24} by 1.9 and 1.6-fold, respectively. The absolute bioavailability was about 16% in a study of 100 mg 'cold' YF476 by mouth after fasting and 15 μ g ^{14}C -YF476 intravenously. Protein binding in human serum was about 84%. In a 7-day study of 100 mg YF476 twice daily of the 1996 formulation, YF476 reached steady state by Day 3 and did not accumulate by Day 7. Even though the crystalline formulations were much less bioavailable than the spray-dried formulations, the pharmacodynamic results were still favourable, which suggests that YF476 is a potent gastrin antagonist in man.

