8.7 Withdrawal of patients from the trial

8.7.1 *Termination of study medication*

Patients may stop taking study medication for the following reasons.

- When a patient has completed the protocol-prescribed treatment, we will not provide any further study medication.
- If a patient has an adverse event, grade 2 or greater (see section 11.1), the patient or investigator may choose to terminate study treatment.
- A patient might be non-compliant and stop taking the protocol-prescribed treatment; or the investigator may choose to terminate study treatment.
- The investigator may terminate study treatment because of a medical contraindication.
- The investigator may terminate study treatment because of evidence of serious interactions with medications metabolized by CYP3A4/5 or CYP2C8, (see Appendix B for list of relevant medications).

In all cases listed above, patients will continue to be followed, if possible, for safety reasons and in order to collect endpoint data according to the schedule of events.

8.7.2 **Termination of study participation**

Patients may go 'off-study' (ie leave the study with no follow-up possible) for the following reasons.

- The protocol treatment and any protocol-required follow-up period is completed.
- If a patient has an adverse event, grade 2 or greater (see section 11.1), the patient may choose to terminate study participation.
- A patient might be lost to follow-up, if the investigator is unable to establish contact with him or her.
- A patient might be non-compliant and not attend the clinic visits (including the follow-up visit).
- The investigator may terminate study participation because of a medical contraindication.
- A patient may withdraw his or her consent to participate in the study.
- Determination of ineligibility, not discovered before enrollment. In particular; patients will be withdrawn from the study if their baseline endoscopy (Visit 2):
 - does not show any intestinal metaplasia; or
 - biopsies are read as indefinite for dysplasia, low grade dysplasia, high grade dysplasia, or adenocarcinoma.
- Death.

8.8 **Study termination**

Enrollment of patients onto the study will be terminated when at least 20 participants have completed 12 weeks of treatment, undergone a post-treatment endoscopy, and returned for the follow-up visit (4 weeks after stopping study medication). The study will end when the analysis of all biopsy samples is complete.

9 **Criteria for evaluation and endpoint definition**

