### **14.1 Extent of Exposure**

The dates and times of first and last treatment dosing will be listed to indicate exposure to the study medication.

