## **16 Pharmacokinetic Analyses**

Analytics Services International Ltd. will measure the plasma concentrations of netazepide. The pharmacokinetic analysis will be done by HMR.

PK data will be summarised using the safety population for patients who received netazepide 25 mg.

For all variables N (number of patients receiving the treatment in the population), n (number of observations), arithmetic mean, median, minimum, maximum, SD, %CV, and the 95% confidence interval for the arithmetic mean will be provided.

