## 17 Changes from the Protocol Specified Statistical Analysis

After the study was submitted to the regulatory authorities and ethics committee the following changes were made to the analyses:

- Section 13.1 Analysis Sets of the protocol states “The pharmacokinetic analysis set will include all patients who receive at least one dose of study medication, and yield at least one plasma concentration for netazepide.” This definition is not included in the SAP as the population is not required.

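### Ctrough is summarised with no condition on time since the last dose or on being on drug, so samples at about 12 h and off-drug samples can enter the trough summary

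*Protocol*

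**What the plan says.** Trough and peak YF476 concentrations are secondary endpoints (Protocol 9.2, SAP 4.2.2).

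- **Dosing time.** Protocol 6.2 instructs: "Study medication should be taken once daily, in the morning, with breakfast". It then says that when someone "takes the study medication without food, or at a different time of the day, it will not be recorded as a protocol deviation". By contrast, missed doses are deviations.
- **The trough sample.** Protocol 8.1 (footnote 3), 8.3 and 8.4 define it as the fasting sample drawn before the clinic dose at Weeks 6 and 12. Patients are told not to dose at home on the visit day. Nothing is said about when the dose before that should have been taken.
- **Patients who stop drug.** Protocol 8.7.1 says that "patients will continue to be followed, if possible, for safety reasons and in order to collect endpoint data according to the schedule of events". That schedule includes the YF476 samples.
- **Who is summarised.** SAP 16: "PK data will be summarised using the safety population for patients who received netazepide 25 mg". SAP 9 defines the safety population by randomisation and at least one dose. SAP 12.1 keeps patients who stop study drug in the analyses, and SAP 12.3 analyses safety-population data as recorded, whatever the visit window.
- **What is listed.** The PK listing shell (L_PK1) has date, planned relative time and the two concentrations. For exposure, SAP 14.1 states: "The dates and times of first and last treatment dosing will be listed".

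**The concern.** With once-daily dosing, a trough concentration means the level about 24 h after the previous dose. The documents fix only the later end of that interval: the sample precedes the next dose.

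A patient who has settled into evening dosing and follows every visit instruction gives a morning sample at about 12 h. No deviation is raised, and the value is labelled Ctrough. A patient who has stopped drug but still attends gives a value close to zero under the same label. No PK rule separates either from a true trough, and the PK listing does not let a reader see which is which.

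At stake is the meaning of the trough summary. With about 10 netazepide patients, a few mistimed samples can move the mean a good deal.

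**Working it through.** The plan gives no figure for trough concentration, so there is none to reproduce. Its one design calculation, the Ki67 power table, does not bear on this point.

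**Inputs**
- Half-life: Protocol 3.2.2 says that it "after 100 mg YF476 was about 7 h". The same section says half-life varied with dose and gives no value for 25 mg. Range assumed here: 5 to 10 h.
- Netazepide patients: 10, from the planned 10 per arm (Protocol 13.7).
- Interval for an evening doser seen in the morning: about 12 h (assumed; the documents give no clinic hour).
- Number of evening dosers: not in the documents. 2 and 3 of 10 are illustrations only.

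**Step 1: one mistimed sample.** Assuming log-linear decline after absorption, with everything but timing equal, C(12 h)/C(24 h) = 2^(12/t½).

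| t½ | C(12 h)/C(24 h) |
|---|---|
| 5 h | 2^(12/5) = 5.28 |
| 7 h | 2^(12/7) = 3.28 |
| 10 h | 2^(12/10) = 2.30 |

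**Step 2: effect on the mean.** If m of 10 samples are at 12 h and the rest at 24 h, the arithmetic mean is multiplied by (10 − m)/10 + (m/10) × ratio.

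| t½ | m = 2 | m = 3 |
|---|---|---|
| 5 h | 0.8 + 0.2 × 5.28 = 1.86 | 0.7 + 0.3 × 5.28 = 2.28 |
| 7 h | 0.8 + 0.2 × 3.28 = 1.46 | 0.7 + 0.3 × 3.28 = 1.68 |
| 10 h | 0.8 + 0.2 × 2.30 = 1.26 | 0.7 + 0.3 × 2.30 = 1.39 |

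At 7 h the geometric mean moves less: 3.28^0.2 = 1.27 for m = 2 and 3.28^0.3 = 1.43 for m = 3.

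**Step 3: off-drug samples.** Relative to the 24 h value at a half-life of 7 h, a sample 48 h after the last dose is 2^(−24/7) = 0.09, and one at 72 h is 2^(−48/7) = 0.009. A patient who stopped well before the visit therefore contributes almost nothing. One such patient in 10 lowers the arithmetic mean by about 10%, and two by about 20%.

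**Step 4: does any rule in the plan remove these samples?** Evening dosing is not a deviation, so a deviation review would not pick it up. Missed doses are deviations, but nothing links them to PK. The pre-lock review in SAP 13.2 may exclude data from analysis populations, but its list of major deviations names neither dose timing nor stopping drug. The safety population depends only on randomisation and having had a dose. No rule removes them.

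**The case against.** The strongest reply is that a patient who follows the instructions gives a sample at about 24 h. Morning dosing is the instruction, and the visit-day dose is held for the clinic. That stands. A reader might infer that patients are free to dose whenever they like; Protocol 6.2 only tolerates another time without logging it. The 12 h case needs a departure from the instruction, and nothing says how common that is.

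Other stronger readings also go too far:

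- **That SAP 17 caused the gap by dropping the PK analysis set** ("This definition is not included in the SAP as the population is not required"). The set in Protocol 13.1 required only one dose and one concentration. It had no timing or on-drug condition, so removing it changed nothing here.
- **That the dose before the PK visit can appear in no output.** Collection date and time are logged for every specimen (Protocol 10.3.2), the diary records study drug daily (Protocol 4.1), and SAP 19.1 promises complete listings of all collected data. Whether the diary captures clock time is not stated. What can be said is that the PK listing shell does not show time since dose.
- **That mistimed troughs would hide non-compliance.** Compliance is measured by capsule count and diary (Protocol 6.7). An evening doser who missed the last dose would be sampled at about 36 h, giving 2^(−12/7) = 0.30 of the 24 h value at a 7 h half-life, which looks low rather than normal.
- **That the exposure-response displays are compromised.** The SAP 16.1 scatterplots use peak concentrations.

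Off-drug samples could also be identified from compliance and withdrawal data. That is true, but being identifiable is not a rule for the summary.

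**Conclusion.** The point holds in a limited form. Followed as written, the plan summarises every available pre-dose sample from netazepide-treated safety-population patients as Ctrough, whatever the time since the last dose and whether or not the patient is still on drug. The PK listing shell would not reveal it.

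Per sample, the error is about 3.3-fold upward for a 12 h draw at a half-life of 7 h, with a range of 5.3 to 2.3 for the assumed 5 to 10 h. For an off-drug draw the value is near zero. The rise in the mean of about 46% (2 of 10) or 68% (3 of 10) at 7 h illustrates assumed shares. Neither is an estimate for this trial, because the true share cannot be derived from the documents.

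The consequence is confined to the descriptive trough summary, a secondary endpoint. Ki67, the sample size and the safety analyses are untouched. It is worth correcting because the correction is cheap.

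**What to change.** 1. Record on the CRF the date and clock time of the last dose taken before each PK draw at Weeks 6 and 12.
2. Add the last-dose date and time and the actual time since dose to listing L_PK1, using the collection times already logged. The SAP's adverse event and concomitant medication listing shells already have a column for time since last dose, so this follows existing practice.
3. State in SAP 16 that only samples from patients on drug, drawn within a stated window around 24 h after the previous dose, are summarised as Ctrough. The sponsor should choose the window before unblinding. Samples outside it, or taken after stopping drug, are listed with their actual time since dose and flagged as not trough.

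The dosing instruction in Protocol 6.2 does not change. If the last-dose time was not captured for some patients, say so and flag those samples rather than assume 24 h.

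The cost is one data field, two listing columns and one SAP sentence. The downside is a slightly smaller n in the trough summary.
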